The design will allow us to find out how effective the treatment actually is in routine everyday practice. Ethically, this randomized controlled trial can only be undertaken if there is collective scientific uncertainty about which of the interventions being compared is more likely to benefit patients. However, for an individual clinician to be able to recommend enrolment of a patient into a trial, they must be substantially uncertain about the appropriateness of the trial treatment in that particular patient. The eligibility criteria for the DEXCON trial are based on this uncertainty principle. A patient can be enrolled only if the responsible clinician is substantially uncertain as to which of the trial treatments would be most appropriate for that particular patient. Using the uncertainty principle should allow the process of this trial to be closer to what is customary in normal medical practice.

Eligible patients

Adults with TBI who fulfill the following inclusion criteria are eligible:

- Patients who have suffered a head injury and have one or more cerebral contusions with visible pericontusional edema in the CT scan.
- Patients with brain contusions in whom non-surgical treatment has been selected initially.
- Age 18 or over and under 85
- Signing of informed consent by the patient or by his legal representative.

The fundamental eligibility criterion is the responsible clinician's 'uncertainty' as to whether or not to use dexamethasone in a particular patient with TBI. This pragmatic approach will allow us to see whether the intervention improves patient outcomes under real-life conditions.

The exclusion criteria are the following:

- Patients with TBI and brain contusions who have required surgery to evacuate the cerebral contusion before randomization.
- Patients with TBI who have required a craniotomy before randomization for any other reason: evacuation of subdural, epidural hematoma or depressed skull fracture.
- Patients with an extracranial Injury Severity Score greater than 18 points.
- Patients in whom the use of corticosteroids is contraindicated.
- Patients who take oral corticosteroids chronically.
- Patients included in another clinical trial.
- Known intolerance or hypersensitivity to dexamethasone.
- Patients with allergy or intolerance to the following excipients contained in dexamethasone / placebo capsules: lactose, corn starch or microcrystalline cellulose.
- Patients with a history of psychotic disorders.

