The GCS score is a method of assessing the level of consciousness in TBI patients. Patients with a GCS score of 15 are generally considered fully conscious, but those with a GCS score of 14 or less may not be fully conscious and would not be mentally capable of giving informed consent to participation in a clinical trial. Besides, a brain contusion is a clinical sign indicating significant brain injury, and patients with this diagnosis would not be physically or mentally capable of giving informed consent to participation in a clinical trial.

Therefore, given that patients are eligible for inclusion in the DEXCON TBI trial if they have a TBI and have a brain contusion on a CT scan, in most cases they will, by default, be physically or mentally incapable of giving consent.

Prior information giving to the patient's relatives

If relatives are present, they will be provided with brief information about the trial. Specifically, the responsible doctor will explain to the relatives that the patient will receive the usual treatments for traumatic brain injury but that, in addition to these, the patient has been enrolled in a research study that aims to improve the treatment of patients with this condition.

It will be explained that the study is being done to see whether using a drug called dexamethasone will help patients with head injury by reducing the amount of edema and inflammation into the brain, therefore preventing further brain damage. The relative will be informed that the patient will be given a treatment over 12 days of either dexamethasone or a dummy medicine (a capsule which does not contain dexamethasone). The doctor will explain that dexamethasone has been shown to improve outcome in patients with other types of brain injuries, such as tumors, and that, whilst we hope that it will also improve recovery after head injury, at present we cannot be sure about this. If requested, a brief information sheet will be provided. If relatives object to the inclusion of the patient in the trial, their views will be respected. If no relatives are present, the patient can not be included in the study.

Treatment

Dexamethasone will be compared with matching placebo.

Dose selection

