Dexamethasone doses are those commonly used in neurooncology and there is an extensive experience in its use. It will be a short and descending course: 4mg/6 hours (2 days); 4 mg/8 hours (2 days); 2 mg/6 hours (2 days); 2 mg/8 hours (2 days); 1 mg/8 hours (2 days); 1 mg/12 hours (2 days).

Drug manufacture, blinding and supply of trial treatment

Dexamethasone (Forteocortin®) will be acquired from ERN, SA. Laboratories (Barcelona, Spain). The Son Espases Pharmacy Department will be in charge of developing and conditioning the 4mg, 2mg and 1mg dexamethasone / placebo capsules needed for 12 days of treatment, keeping the researchers blind.

The preparation and conditioning of the capsules will be carried out following the standardized work procedures of the pharmaceutical laboratory and its quality controls, previously authorized by the Agencia Española del Medicamento (AEMPS).

The Son Espases Pharmacy Department will be responsible for identifying the containers and sending them by courier to the participating hospitals. A record of the dispensing of test samples will be kept and will be sent in acknowledgment of receipt for control.

Patients, clinical staff, evaluators of the results as well as the statistical team that will perform the analysis will not know the assigned treatment. A randomization list will be created for each hospital. The randomization sequence will only be known by the Pharmacy Department of Son Espases Hospital.

Administration of trial treatment

Each patient will receive 3 containers with the correspondingly identified doses, and an information sheet explaining dose and frequency for proper oral administration.

Other treatments for traumatic brain injury

There is a wide spectrum of treatments for TBI. As the trial will be conducted in Spain, each participating site should follow its own clinical guidelines for the treatment of TBI patients. There is no need to withhold any clinically indicated treatment in this trial.

Dexamethasone or placebo would be provided as an additional treatment to the usual management of TBI.

Safety and Adverse events

Dexamethasone has a well documented safety profile. Nevertheless, data on adverse events, such as infectious complications, hyperglycemia, gastro intestinal bleeding or appearance of psychotic symptoms will be collected as secondary outcomes and will be presented to the independent Data Monitoring Committee (DMC) for blinded review.

Definitions

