This procedure will be performed again centrally in the 12 de Octubre hospital, Madrid. Previously, the patient's data will be anonymized and the images will be sent through a web platform with a secure server for review. In a central way, the total volume of the contusion will be established as well as the volume of the edema by means of a semi-automatic method using the Analyze software (vesion 10.0; Analyze Direct, Stilwell, Kansas, USA) of which a license is available. The method consists of a semi-automatic analysis in which in each axial section a central voxel is selected and thanks to the density selection, voxels with similar density characteristics are selected.

The performance of measurements in each hospital and subsequent centralization of the images will allow to establish the interobserver and intermethod reproducibility of the measurement of the edema associated with the contusions, in addition to estimating in two ways the difference of measurements at two time points throughout the study and after an intervention.

-Compare the presence of adverse events between the two groups during the 12 days of treatment.

Those adverse effects that have special interest and serious adverse effects will be collected. Side effects of special interest are:

-Metabolic: Hyperglycemia will be especially monitored. The maximum value of capillary glycemia will be recorded daily. The amount of daily insulin that the patient needs to control de glucose level will also be collected.

-Psychiatric: presence of psychotic symptoms using the Confusion Assessment Method (CAM).

-Digestive: Episodes of gastro intestinal hemorrhage; Episodes of epigastric pain, vomiting or reflux symptoms.

-Infectious: Presence of new infectious episodes. Infectious episode will be confirmed in accordance with the Centers for Disease Control (CDC) criteria and mainly based on microbiological criteria.

- Compare the results of the neuropsychological tests between the two groups of patients one month and 6 months after the TBI.

Two neuropsychological evaluations will be performed: 1 month and 6 months after the TBI. Both evaluations will be performed by clinical neuropsychologists, and the protocol to be used will always follow the same procedure and tests. The tests that integrate this protocol are described below:

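### The psychotic-symptom safety outcome is measured only with a confusion instrument, so confusion from the injury would dilute any true difference between arms

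*Combined protocol and SAP*

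**What the plan says.** The Safety and Adverse events section lists the harms to be tracked and sent to the DMC, and among them "appearance of psychotic symptoms will be collected as secondary outcomes". The exclusion criteria under Eligible patients include "Patients with a history of psychotic disorders", so psychosis is treated as a relevant risk. Supplemental data 1 sets the comparison ("Compare the presence of adverse events between the two groups during the 12 days of treatment") and defines the psychiatric event of special interest as "presence of psychotic symptoms using the Confusion Assessment Method (CAM".

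That is the whole definition. The text gives no CAM version, assessor, frequency, baseline assessment, category for patients who cannot be assessed, or rule separating psychotic symptoms from confusion. Neighbouring items say more: for glucose, "The maximum value of capillary glycemia will be recorded daily", and infections must meet named confirmation criteria.

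On the population, the section on ethical considerations and consent says that "those with a GCS score of 14 or less may not be fully conscious" and that "in most cases they will, by default, be physically or mentally incapable of giving consent".

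**The concern.** The label and the instrument name different things. One is psychosis, a recognised concern with the study drug. The other is confusion, which a brain contusion can cause without any drug. If the event is counted as written, a patient confused by the injury can enter the safety table under psychotic symptoms in either arm. That background adds noise and shrinks the between-arm difference in the harm of interest. No baseline CAM is stated, so confusion already present at entry cannot be removed.

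At stake is the reading of one named safety outcome, both in the final comparison and in what the DMC reviews. The efficacy endpoint is not measured with the CAM.

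**Working it through.** The documents give no rate for psychosis or confusion and no sample size for this outcome. The psychosis and confusion rates below are therefore **assumptions**, shown over a range. The plan also names no formal test for this outcome, so power serves here only as a measure of lost information.

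**1. The plan's own figure, to fix the arm size.** The inputs come from the sample size section: 50% v 62%, two-sided 5%, 80% power, 10% inflation. Allocation is 1:1 (Randomization, blocks of 2).

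n per arm = [1.96·√(2·0.56·0.44) + 0.8416·√(0.50·0.50 + 0.62·0.38)]² / 0.12² = 267.4, so 268. The total is 536, and 536/0.9 = 596, which agrees with the stated 600. With 10% lost, 600 × 0.9 / 2 = 270 per arm.

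**2. Psychosis measured directly.** Assume 2% on placebo and 6% on dexamethasone.
- SE under the null = √(2·0.04·0.96/270) = 0.01687
- SE under the alternative = √[(0.02·0.98 + 0.06·0.94)/270] = 0.01678
- Power = Φ[(0.04 − 1.96·0.01687)/0.01678] = Φ(0.41) = 66%

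**3. Psychosis measured by the CAM.** Let c be confusion from the injury, q true psychosis, and s the share of psychotic patients who score positive, with confusion and psychosis independent. Then P(CAM+) = 1 − (1 − c)(1 − s·q). With the same c in both arms, the difference is s·(1 − c)·(6% − 2%), always smaller than 4 points when c > 0. For c = 20% and s = 1: 1 − 0.80·0.98 = 21.6% and 1 − 0.80·0.94 = 24.8%.

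| Background confusion | CAM+ placebo (s = 1) | CAM+ dexamethasone (s = 1) | Difference (s = 1) | Power (s = 1) | Difference (s = 0.5) |
|---|---|---|---|---|---|
| 20% | 21.6% | 24.8% | +3.2 points | 14% | +1.6 points |
| 30% | 31.4% | 34.2% | +2.8 points | 10% | +1.4 points |
| 50% | 51.0% | 53.0% | +2.0 points | 7% | +1.0 points |

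The s = 1 columns are the best case for the CAM. With s = 0 the difference is nil. Assuming 3% v 8% instead, direct power is 72%, and CAM power (s = 1) is 0.190, 0.135 and 0.084 at the three backgrounds.

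**4. What it would take to reverse the sign.** Suppose dexamethasone also lowers confusion. The dexamethasone-arm confusion rate that cancels the signal is c₁ = 1 − (1 − c)(1 − 0.02s)/(1 − 0.06s). For c = 20% and s = 1: 1 − 0.80·0.98/0.94 = 16.6%, a relative fall of 3.4/20 = 17%.

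| Background confusion | Cancelling relative fall, s = 1 | Cancelling relative fall, s = 0.5 | CAM difference if confusion falls 20% relative (s = 1) |
|---|---|---|---|
| 20% | 17% | 8% | −0.6 points |
| 30% | 10% | 5% | −2.8 points |
| 50% | 4% | 2% | −7.4 points |

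With 3% v 8% psychosis the cancelling falls at s = 1 are 22%, 13% and 5%.

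**The case against.** Four points can fairly be made for the plan.

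- **Reporting rule.** The section on reporting adverse events limits the reporting form to events reasonably attributable to the trial drug and leaves out expected complications of TBI. On that wording, drowsiness from the contusion might never be counted. This softens the point, but the documents never say how the rule applies to a positive CAM.
- **Another route.** Serious adverse effects are collected, and a serious adverse event needs a written report within 24 hours. Severe psychosis could reach the DMC that way. This stands, so the safety net is weakened but not absent. It catches only serious cases and is not the comparison labelled psychotic symptoms.
- **Unknown background.** A reader might infer that most participants will not be fully conscious. The consent section does not say so. It says that patients at or below a certain score may not be, and that most will be incapable of consent for physical or mental reasons. No distribution of coma scores and no confusion rate is given, and patients are expected to rate 16 symptoms daily. How large the dilution is therefore remains unknown.
- **Content of the instrument.** A reader might also infer that a psychotic patient with clear attention would score negative. That needs the CAM's item content, which the documents do not give. The argument rests on the instrument's name, and the main calculation lets every psychotic patient score positive.

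The assessment schedule in Figure 2 is not available here. Its legend does not list the CAM, and a schedule would not change what the instrument measures.

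**Conclusion.** The concern holds as a mismatch between a named safety outcome and its only stated measure. If events are counted as written, dilution follows whenever some patients are confused from the injury. Under the assumed 2% v 6%, power falls from about 66% to between 14% and 7% over backgrounds of 20% to 50%, in the best case for the CAM. These figures rest on assumed rates, independence of confusion and psychosis, and 270 evaluable patients per arm.

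A reader might go further and infer that the trial would show fewer psychotic symptoms on the steroid while true psychosis rose. The documents do not support that as an expectation. Reversal needs dexamethasone to reduce confusion by more than the cancelling falls shown above. Such an effect fits the trial's rationale of less edema and inflammation, but it is not shown. Nor do the documents support saying that the DMC would see nothing of psychosis, because serious cases have a separate route.

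The point concerns one category within a secondary outcome. It is a cheap improvement.

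**What to change.** In Supplemental data 1:

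1. Report the CAM result under its own name, as confusion or delirium.
2. Define psychotic symptoms as a separate yes/no event: new hallucinations, delusions or manic symptoms since the pre-treatment assessment, with an unable-to-assess category. Record it at contacts already described there, either the neurological exams three times a day or the daily Rivermead questionnaire, and compare it between arms.
3. State how the exclusion of expected TBI complications, in the section on reporting adverse events, applies to a positive CAM.

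The third item also matters for the analysis set. The section on end of trial for participants ties an adverse event to stopping the trial drug, and the Analysis section removes patients who did not complete 12 days. If a positive CAM counted as an adverse event, confusion from the injury could affect who is analysed, so these sections need to be reconciled.

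The cost is one or two extra form items and no additional patient contact. The documents describe no daily CAM form, so the items have to be added to whatever is used at those contacts. The downsides are reliance on bedside observation and a lower event count than the CAM would give.
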